II. Appendices:.....	33

I. Study Synopsis

Study Title	N-Force Screws augmented with N-Force Blue in Intracapsular Proximal Femur Fracture Treatment
Abbreviated Study Title	N-Force Study
Sponsor	Zimmer Biomet, Warsaw, Indiana
Protocol Number	CMU2017-60T
Anticipated Start Date	Q4 2018
Study Objectives	
The objective of this prospective study is to confirm safety and performance of N-Force Screws augmented with N-Force Blue applied in intracapsular proximal femur fracture treatment.
 
Further results will be compared to non-augmented standard cannulated screws (historic control).
 
Primary Endpoint:
 
 • Re-operation within 12 months after initial surgery to promote fracture healing, relieve pain, treat infection, or improve function^[4]. 
Secondary Endpoints:
 
 • Radiographic and clinical fracture healing of the proximal femur using standard scoring methods and patient satisfaction. • Cost effectiveness
Target Population	Patients with primary Garden I and II intracapsular proximal femur fractures requiring surgical intervention and eligible for fixation by three cannulated screws augmented with N-Force Blue.
Study Design	Multicenter, prospective, non-controlled clinical study
Study Type	Post-market clinical follow-up study (PMCF)
Sample Size	190 Subjects (151 + 20% anticipated lost to follow-up)
Length of Study	3 years (1 year enrollment, 1 year follow-up and 1 year study close-out)
Follow-up Intervals	6 weeks, 3 months, 6 months and 12 months after surgery
Inclusion/Exclusion Criteria	
Inclusion Criteria:
 
 • Patient has primary Garden I or II intracapsular proximal femur fracture requiring surgical intervention and is eligible for fixation by three cannulated screws augmented with N-Force Blue.

	
 • Patient receives operative treatment within 7 days of injury. • Patient was ambulatory before injury. • Patient is 50 years of age or older. 
Exclusion Criteria:
 
 • Patient has Garden III or IV intracapsular proximal femur fracture. • Patient has major cognitive impairment (including dementia). • Patient is on dialysis. • Patient is not expected to survive follow-up schedule. • Patient is expected to have problems maintaining follow-up compliance, i.e. patients with no fixed address, patients not mentally competent to give informed consent, etc. (Investigator's discretion). • Patient is a prisoner. • Patient is known to be pregnant and/or breastfeeding. • Patient is a known alcohol or drug abuser. • Patient had previous/has active acute or chronic infections, especially at the site of operation. • Patient has non-viable bone, or has areas where surrounding bone is not viable or capable of supporting and anchoring the implant. • Patient has traumatic injuries with open wounds or close to the proximal femur fracture, which are likely to become infected. • Patient is expected to be non-compliant with recommended post-operative weight-bearing instructions. • Physical conditions, in the opinion of the investigator, that would prohibit adequate implant support or impede healing.
Study Device	N-Force Fixation System 7.3 mm (Non-fenestrated/fenestrated) applied with washers; N-Force Blue (Bone Substitute Material)
Outcome Measures	
 • RUSH Score • FIX-IT • Avascular necrosis (Steinberg classification) rate at 12 months follow-up • Harris Hip Score • Timed "Up-And-Go" Test • EQ-5D-5L • Adverse Events

Documentation	Electronic Case Report Forms
Statistical Reporting	Data collected will be summarized and reported to each participating investigator. Statistical analysis will be conducted by Zimmer Biomet or its designee.

This protocol is compliant with ISO 14155 Standard for Clinical Investigation of Medical Devices For Human Subjects – Good Clinical Practice ^[1] , is in accordance with US Code of Federal Regulations 21 CFR Parts 11, 50 and 56 ² , and The Declaration of Helsinki (DoH) – Ethical principles for medical research involving human subjects.

II. Data Collection Overview

The following table indicates the necessary case report forms to be completed at the given time point:

Form Name	Pre-op	Operative & Discharge	6 weeks Post-op (± 14 days)	3 months Post-op (± 30 days)	6 months Post-op (± 60 days)	12 months Post-op (± 90 days)	Revision
Informed Consent	X						
Inclusion/Exclusion Criteria	X						
Demographic Evaluation	X						
Operative & Surgical Device Information		X					
Postoperative Discharge Assessment		X					
Timed "Up and Go" Test			X	X	X	X	
X-rays (A/P and Lateral – Operated Side)	X	X	X	X	X	X	X
EQ-5D-5L			•	•	•	•	
Postoperative Follow-Up			X	X	X	X	
FIX-IT Score			X	X	X	X	
Harris Hip Score			X	X	X	X	
Study Completion		*	*	*	*	*	X
**Adverse Event (Complication)	*	*	*	*	*	*	X
Protocol Deviation	*	*	*	*	*	*	*
Physician Radiographic Assessment (including RUSH)			*♦	*♦	*♦	*♦	*♦
Steinberg Classification						*♦	
Explanted Device		*	*	*	*	*	*

X Completed by Investigator or Designee (required)
 • Completed by Patient
 * Completed by Investigator or Designee (as applicable)
 ♦ Independent radiographic review may be performed by Sponsor's designee if requested by the Sponsor.
 ** If device related Adverse Event occurs, a Product Experience Report (PER) must be completed and forwarded to the sponsor within 7 days of occurrence. Supporting documents must be sent to the sponsor as well and include the Operative Report (index and revision) and Radiographs (immediate post-op, all follow-up visits, and pre-revision).

III. Introduction and Purpose

Intracapsular Proximal Femur Fractures are a common injury especially in the elderly population. Optimal treatment remains controversial. Frequently applied operative treatments include three cannulated screws, sliding hip screw, hemi- and total arthroplasty. AAOS Guidelines for femoral neck fractures in the elderly recommend operative fixation for stable non-displaced fractures and arthroplasty for unstable displaced fractures. In a recent landmark randomized trial including more than one thousand patients comparing sliding hip to cannulated screws, every fifth patient had to be repeated to promote fractures

healing [4]. Reoperation rates of 20% for sliding hip screw and 22% for cannulated screw were found; however, the difference was not statistically significant.

Zimmer Biomet offers a Hip Screw technology that is capable of delivering a Bone Substitute Material (BSM) to the fracture-implant interface for fixation of fractures of the femoral neck [5][6]. This device allows hard setting BSM to the precise location, providing a multi-dimensional fixation that is critical to reduce the chance of joint collapse and articular fragment displacement and ultimately could reduce the high reoperation rates reported for this kind of injury.

This study will assess the reoperation rates, including revision, and document the clinical and radiographic outcomes of hip fracture patients, utilizing the N-Force Fixation System. Results will be compared to “standard” non-augmented cannulated screw (historic control).

IV. Study Objectives

The objective of this prospective study is to assess safety and performance of N-Force Screws augmented with N-Force Blue applied in intracapsular proximal femur fracture treatment. Further results will be compared to non-augmented standard cannulated screws (historic control).

Safety: Will be assessed by monitoring the frequency and incidence of adverse events (AE), serious adverse events (SAE), adverse device effects (ADE), serious adverse device effects (SADE), and unanticipated serious adverse device effects (USADE) and device deficiencies.

Performance: Will be determined by analyzing the fracture healing (union) rate at 6 weeks, 3 months, 6 months, and 12 months postoperatively.

The primary endpoint of this study is defined as re-operation within 12 months after initial surgery. Reoperation is defined as a second surgery to correct the previous procedure or the complications of a previous surgery. For this study, reoperation will include second surgeries to promote fracture healing, relieve pain, treat infection, or improve function including:

- Removal of the implant prior to fracture healing
- Internal fixation with another implant during revision surgery
- Revision to total hip arthroplasty
- Incision and drainage or other soft tissue procedure due to deep infection at the bone implant interface.

Secondary endpoints of this study include:

- Clinical (FIX-IT) and radiologic (RUSH)^{[8][9]} fracture healing at 6 weeks, 3, 6 and 12 months post-surgery.
- Length of femoral neck ^{1.a.[7]}
- Proportion of patients with avascular necrosis at one year FUP (Steinberg classification)
- Functional Index for Trauma (FIX-IT)^[10]
- Harris Hip Score^[11]
- Timed “Up-And-Go” Test^[12]
- EQ-5D-5L
- Adverse events (complications)

Additionally, a cost effective analysis comparing N-Force to standard non-augmented cannulated screws will be performed.

It is planned that once sufficient data has been collected allowing meaningful statistical analysis, contributing investigators can use the data for peer reviewed publications, podium presentations and as a basis for surgeon discussions and learning.

V. Study Design

This is a prospective, multicenter, non-controlled clinical study designed to facilitate the collection and evaluation of fracture healing, pain, function, quality of life, radiographic assessment, and adverse event data. A maximum of 16 sites will contribute to this study. Enrollment per site will be approximately 12 implanted devices with a site maximum of 47 (25% of total study population). Each Investigator will be skilled in proximal femur fracture treatment and experienced implanting the devices included in this study, as determined by the Sponsor.

Each Principal Investigator will be responsible for obtaining Institutional Review Board (IRB) or Ethics Committee (EC) approval as required prior to conducting the study. In order to avoid potential selection bias, each Investigator will offer study participation to each consecutive eligible patient presenting as a candidate for proximal femur fracture treatment using the commercially available (FDA cleared) N-Force Screws augmented with N-Force Blue. Eligible candidates who express interest in study participation will be offered Informed Consent. All potential study subjects will be required to participate in the Informed Consent process and will not be considered enrolled in the study until the candidate has signed and dated the IRB/EC approved patient Informed Consent. Study data cannot be collected until the candidate has completed the informed consent process and signed and dated the IRB or EC approved Informed Consent.

Once Informed Consent has been obtained, preoperative, operative, and discharge documentation will be collected either via retrospective chart review or direct interview

with the subject. Patients who have previously received N-Force Screws augmented with N-Force Blue may be enrolled in the study if informed consent occurs prior to the end of the 6 weeks follow-up visit window. This will include retrospective chart review for pre-operative and operative data for patients who meet the inclusion criteria (and do not meet any of the exclusion criteria) and have available surgical data. Patients that meet these requirements will be asked to consent to study participation postoperatively. The consented patients will be followed prospectively at designated follow-up visits if all appropriate Ethics Committee approvals and patient consent is obtained. The post-operative clinical and radiographic evaluations will be conducted at 6 weeks, 3 months, 6 months, and 12 months post-surgery.

Review of radiographs will be completed by the investigators at each clinical follow-up interval to determine the incidence of loss of reduction, implant migration and radiographic evidence of fracture healing. In addition, the Investigator will review radiographs at each clinical follow-up interval to ensure radiographic evidence of adverse events is documented and reported to the IRB or EC and the Sponsor as required. At the Sponsor's discretion, the Sponsor may request copies of these radiographs for independent radiologic review. The Sponsor may request one central reviewer for all radiographs independent of the surgeon and institution.

VI. Study Population

The study population for primary statistical analysis will be comprised of males and females who require intracapsular proximal femur fracture repair and satisfy the inclusion/exclusion criteria outlined in this section of the protocol. In total, one-hundred-and-ninety (190) patients will be enrolled.

In order to avoid potential selection bias, each Investigator will offer study participation to each consecutive eligible patient presenting as a candidate for intracapsular femur fracture repair using the commercially available (FDA cleared) N-Force Screws augmented with N-Force Blue. Eligible candidates who express interest in study participation will be offered Informed Consent. The **Inclusion/Exclusion Criteria** case report form should not be completed until the study-specific consent form has been completed.

1. Inclusion Criteria

- Patient has primary Garden I or II intracapsular proximal femur fracture requiring surgical intervention and is eligible for fixation by three cannulated screws augmented with N-Force Blue.
- Patient receives operative treatment within 7 days of injury.
- Patient was ambulatory before injury.

- Patient is 50 years of age or older.

Note: Patients who have previously received N-Force Screws augmented with N-Force Blue may be enrolled in the study if informed consent occurs prior to the end of the 6 weeks follow-up visit window.

1. Exclusion Criteria

- Patient has Garden III or IV intracapsular proximal femur fracture.
- Patient has major cognitive impairment (including dementia).
- Patient is on dialysis.
- Patient is not expected to survive follow-up schedule.
- Patient is expected to have problems maintaining follow-up compliance, i.e. patients with no fixed address, patients not mentally competent to give informed consent, etc. (Investigator's discretion).
- Patient is a prisoner.
- Patient is known to be pregnant and/or breastfeeding.
- Patient is a known alcohol or drug abuser.
- Patient had previous/has active acute or chronic infections, especially at the site of operation.
- Patient has non-viable bone, or has areas where surrounding bone is not viable or capable of supporting and anchoring the implant.
- Patient has traumatic injuries with open wounds or close to the proximal femur fracture, which are likely to become infected.
- Patient is expected to be non-compliant with recommended post-operative weight-bearing instructions.
- Physical conditions, in the opinion of the investigator, that would prohibit adequate implant support or impede healing.

*Inclusion/Exclusion criteria address the N-Force Screw, N-Force Delivery System, and N-Force Blue

VII. Study Device Information

The N-Force Fixation System is designed to provide fracture fixation and stabilization of femoral neck fractures by the use of the N-Force 7.3mm Fenestrated and Non-Fenestrated Screws (Figure 1) (N-Force 4.0mm screws will not be used in this study). N-Force 7.3mm is intended for use in the femoral neck fractures of the proximal femur. Washers are available for use with the 7.3mm Screw design.

Figure 1: left 7.3 mm Non-Fenestrated Screw, right 7.3 mm Fenestrated Screw

The N-Force Fixation System Screws and Washers are fabricated from Titanium alloy (Ti-6AL-4V) and are biocompatible for human implantation.

The N-Force Fixation System is designed to be used with the N-Force Blue Mixing & Delivery System (Figure 2). These components are single use instruments designed to be used for the mixing of bone substitute materials.

Figure 2:

The N-Force Blue Porous Bone Substitute material is a synthetic, biocompatible bone graft substitute material that forms a poorly crystalline hydroxyapatite at body temperature. It is provided in a single patient, single use kits in various volumes appropriate to the surgical site.

VIII. Study Procedures

A. Offer Study Participation

Study participation will be offered to each consecutive eligible patient presenting as a potential candidate for intracapsular proximal femur fracture repair using the commercially available (FDA cleared) N-Force Screws with N-Force Blue.

Eligible candidates who express interest in study participation will be offered Informed Consent. Prior to patient involvement in the study, the patient must participate in the Informed Consent process and sign and date the IRB or EC approved Informed Consent.

B. Informed Consent Process

For candidates that express interest, the Investigator or Designee will describe relevant study information, including the purpose, procedures, possible risks, and potential benefits associated with study participation. The Investigator or Designee will also review, along with the candidates, the Informed Consent approved by both the governing IRB or EC and the study Sponsor. Candidates shall have sufficient time to read and understand the IRB or EC approved Informed Consent and discuss whether they wish to participate in the study. Candidates will be asked to acknowledge whether all of their questions and concerns have been addressed to their satisfaction. Any questions that candidates may have will be addressed appropriately by the Investigator or Designee. Candidates will be further instructed that they are free to obtain additional information from the Investigator or Designee at any time, that they are free to decline participation, and that they are free to withdraw their consent and discontinue their participation at any time without prejudice.

After completing the Informed Consent process, candidates who agree to enter the study must sign and date the IRB or EC approved Informed Consent. The Informed Consent must be signed and dated prior to the date of the study surgery for prospective subjects. Subjects enrolled retrospectively may sign and date the Informed Consent after surgery.

A copy of the signed Informed Consent must be provided to the study subject. The original signed Informed Consent is to be filed in the subject's medical record, study subject binder, or regulatory binder.

Study data will not be collected until the Informed Consent has been signed and dated. If the candidate does not wish to participate (does not sign and date the Informed Consent), data for that candidate will not be collected for this study.

C. Informed Consent / Enrollment Log

An **Informed Consent / Enrollment Log** (Appendix C) will be maintained at the site throughout the course of the study. The purpose of the log is to provide documentation that all enrolled study subjects underwent the Informed Consent process, signed and dated the IRB or EC approved Informed Consent, and were provided with a copy of the fully executed consent with all required signatures. All candidates who sign and date the approved Informed Consent for the study must be entered in the log. If a subject signs and dates additional Informed Consent(s) after enrollment (e.g., due to a protocol amendment, protocol

revisions, etc.), subsequent signings will also be recorded in the log. The Informed Consent/Enrollment Log will be filed in the site Regulatory Binder for the study. After a subject receives the study device during surgery, the date of surgery will be added to the log. The subject will now be considered an active study subject. In the event that a subject does not receive the study device at the time of surgery, a **Study Completion** case report form must be submitted and this will be documented as a screen failure on the Informed Consent/Enrollment Log.

D. Subject Enrollment

Once the Informed Consent has been signed and dated by the subject or delegated signatory, the subject will be considered enrolled in the study. A unique case identification number (Case ID) will be assigned to each participating subject/femur (bilateral subjects will be assigned a unique case ID number for each femur). This unique case ID number will be used throughout the study for identification. Case ID numbers will be assigned consecutively in ascending order per site, with the starting number for a given site defined by the Sponsor. In the event that the subject does not receive the study device at the time of surgery, the subject will be considered a screen failure and documented on **the Informed Consent/Enrollment Log** (see above).

E. Monitor Log

The **Site Monitoring Visit Log** (Appendix C) will be maintained throughout the course of the study. The log will contain the visit date, monitor name/signature and the purpose of the visit (i.e. site initiation, onsite interim monitoring (as applicable), site close-out, etc.). The site monitoring visit log will be filed in the site Regulatory Binder for the study.

F. Delegation of Authority (Site Signature Log)

A **Delegation of Authority/Site Signature Log** (Appendix C) will be maintained throughout the study and will contain the names, initials, signatures and study responsibilities of all site personnel/designees involved in study procedures and data collection. This log will be filed in the site Regulatory Binder for the study.

G. Baseline/Pre-operative Assessment

Baseline/pre-operative data will be collected on the following case report forms at the time of enrollment:

1. Informed Consent

2. Inclusion/Exclusion Criteria
3. Demographic Evaluation
4. Adverse Event Report(s) (as applicable)
5. Protocol Deviation(s) (as applicable)

H. Surgical Technique

Standard operative procedures will be followed and all surgical procedures will be performed under aseptic conditions. Investigators will implant all commercially available N-Force Screws with N-Force Blue and any other compatible products in compliance with corresponding labeling requirements and in accordance with appropriate surgical technique(s).

I. Surgical, Immediate Post-surgical Procedures and Discharge (Data Collection)

Surgical and immediate post-surgical data will be collected on the following case report forms:

1. Operative and Surgical Device Information
2. X-rays (AP and Lateral)
3. Postoperative Discharge Assessment
4. Adverse Event Report(s) (as applicable)
5. Protocol Deviation(s) (as applicable)
6. Implanted Device Form (as applicable)
7. Study Completion (as applicable)

J. Post-surgical management

Post-surgical management for study subjects will follow the investigator's standard of care for patients undergoing intracapsular proximal femur fracture. Post-surgical rehabilitative therapy will be as prescribed by the investigator.

K. Post-operative Follow-up Procedures (Data Collection)

Post-operative clinical evaluations/assessments will be conducted at 6 weeks \pm 14 days, 3 months \pm 30 days, 6 months \pm 60 days, and 12 months \pm 90 days post-surgery. The following case report forms will be collected at each interval:

1. Postoperative Follow-up
2. X-rays (AP and Lateral)
3. Physician Radiograph Assessment including RUSH

4. Steinberg Classification (12 months Follow-Up only)

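### The primary analysis set in Section VI depends on meeting the eligibility criteria, but nothing fixes eligibility at enrolment or keeps every implanted subject in, so outcome-informed exclusion is not prevented

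*Combined protocol and SAP*

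**What the plan says.** Section VI (Study Population) opens with the only statement in the document about who enters the primary analysis. That population is to consist of "males and females who require intracapsular proximal femur fracture repair and satisfy the inclusion/exclusion criteria outlined in this section of the protocol". Section XI (Statistical Considerations) defines no analysis set. Its sample-size paragraph speaks of 151 evaluable subjects without saying what makes a subject evaluable.

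The exclusion criteria in Section VI include "Physical conditions, in the opinion of the investigator, that would prohibit adequate implant support or impede healing", "Patient has non-viable bone, or has areas where surrounding bone is not viable or capable of supporting and anchoring the implant" and "Patient has Garden III or IV intracapsular proximal femur fracture".

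On timing, Section VIII.G lists the Inclusion/Exclusion form among the baseline forms: "Baseline/pre-operative data will be collected on the following case report forms at the time of enrollment". Section VIII.B adds: "The Informed Consent must be signed and dated prior to the date of the study surgery for prospective subjects". Sections V and VI also admit patients who already have the implant, provided they consent before the 6-week visit window closes, and Section VI has the eligibility form completed only after consent. Section IX.D.4 lets the investigator withdraw a subject judged to have ceased to meet the criteria, and sets no time limit. Sections VIII.C and VIII.D treat a consented subject as a screen failure only if the device was not implanted.

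**The concern.** The study has one arm, is unblinded, and is read against an external reoperation rate. Eligibility decisions made after implantation therefore act directly on the observed rate, with no concurrent control to absorb them.

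The criteria on bone support and on conditions that hinder healing describe ways in which fixation fails. A hip that has failed gives a reason to look again at bone quality or fracture grade; a healed hip gives none. Section IX.D.3 also calls for radiographic findings to be documented before revision surgery, so failed hips receive extra film review. If eligibility is reconsidered more often after failure, and the primary set holds only subjects who meet the criteria, failures would leave the numerator more readily than successes leave the denominator. The plan contains no safeguard against this.

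**Working it through.** **1. When eligibility can be judged, relative to outcome.**

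- Prospective subjects: consent precedes surgery and the eligibility form is a baseline form, so the first record of eligibility precedes any outcome.
- Already-implanted subjects: consent may come as late as 6 × 7 + 14 = 56 days after surgery, and the form follows consent. Eligibility can be recorded with early failure already known.
- All subjects: withdrawal on eligibility grounds (Section IX.D.4) is open throughout follow-up.
- No section says which of these judgements decides membership of the primary set.

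**2. The plan's own sample size.** Section XI.B gives a historical rate p0 = 0.15, an assumed device rate p1 = 0.075, 151 evaluable and 190 enrolled with 20% loss. Alpha, sidedness, power and test are not stated. Assuming a one-sample normal approximation, two-sided 0.05 and 80% power:

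n = [(1.960 × √(0.15 × 0.85) + 0.842 × √(0.075 × 0.925)) / (0.15 − 0.075)]² = [(0.700 + 0.222) / 0.075]² ≈ 151.

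Then 151 / 0.80 = 188.75, or 189, against the stated 190. The figures reproduce, and changing the analysis set does not alter them. Expected reoperations are 151 × 0.075 ≈ 11 at the assumed rate and 151 × 0.15 ≈ 23 at the historical rate, so a handful of exclusions is a material share.

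**3. Effect of dropping failures.** The plan states no success rule. Assume success means that the upper limit of the exact (Clopper-Pearson) 95% interval lies below 15%. Assume also that k subjects are dropped and that all of them were reoperated. The documents give no value for k; the range shown is 0 to 4.

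For each k in this range, 13 remaining reoperations meet the criterion and 14 do not (for example, 14/151 has an upper limit of 15.07%). Success therefore needs at most 13 + k reoperations before exclusion, and its probability is P(X ≤ 13 + k) with X binomial(151, 0.15).

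| k dropped | Limiting result analysed | Upper limit | Reoperations before exclusion | Chance of success at true 15% |
|---|---|---|---|---|
| 0 | 13/151 = 8.6% | 14.27% | 13 | 1.4% |
| 1 | 13/150 = 8.7% | 14.36% | 14 | 2.6% |
| 2 | 13/149 = 8.7% | 14.46% | 15 | 4.6% |
| 3 | 13/148 = 8.8% | 14.55% | 16 | 7.6% |
| 4 | 13/147 = 8.8% | 14.65% | 17 | 11.8% |

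**4. Single results.** One exclusion can matter at the boundary: 14/151 (9.3%, upper limit 15.07%) becomes 13/150 (8.7%, upper limit 14.36%). Away from it, more are needed. From 16/151 (10.6%, upper limit 16.6%), dropping two gives 14/149 (upper limit 15.26%), which still includes 15%; dropping three gives 13/148, which does not.

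**The case against.** The sentence heads a section on the study population, is followed at once by the enrolment total, and introduces the eligibility list. It can fairly be read as saying who is recruited. A reader might infer something stronger: that the plan directs implanted subjects to be re-judged after failure and removed, or that the reported rate will be biased low. The documents do not support that. No section provides for a later eligibility review that deletes implanted subjects from the analysis. The eligibility form is a baseline form, prospective subjects consent before surgery, and screen failure is confined to subjects who did not receive the device. Protocol deviations are to be documented, with no statement that they lead to exclusion. A revision that removes a study device generates an adverse event form and a completion form, so the failure stays on record.

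The arithmetic is also a worst case. Every dropped subject is a failure, no healed hip is dropped, and the success rule is assumed, since Section XI describes descriptive summaries with 95% intervals.

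All of this stands, and it limits the point to a gap in the wording. It does not close the gap. The sentence names the primary analysis expressly and enrolment has its own sentence. The withdrawal clause and post-operative enrolment show that eligibility judgements after implantation are contemplated. Nothing says that such subjects remain in the analysis.

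**Conclusion.** The point holds as a missing safeguard. The primary set is conditioned on eligibility, some criteria are judgements linked to fixation failure, two provisions allow eligibility to be judged after implantation, and no rule retains every implanted subject. Outcome-informed exclusion is possible and would lower the reoperation rate if it concentrated on failures.

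The table in the working gives the size: a 1.4% chance of apparent success rises to between 2.6% and 11.8%. That range rests on four assumptions: 151 subjects analysed before exclusions, a true rate of 15%, one to four exclusions that are all failures, and a success rule the plan does not state. It shows sensitivity and does not predict what will happen. The documents do not establish that bias will occur. This is a cheap improvement, worth making because the comparison is single-arm and unblinded.

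**What to change.** Replace the opening sentence of Section VI with wording such as: the primary analysis includes every consented subject who received the study device, whatever eligibility deviation is found later; eligibility status is taken from the baseline Inclusion/Exclusion form. Under that rule, a subject withdrawn on eligibility grounds under Section IX.D.4 stays in the set.

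Report the eligible-only set as a sensitivity analysis, and list each subject left out of it with the reason and reoperation status. Marking in that list the subjects who consented after surgery would help, because their form is not completed before the operation.

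The cost is one sentence of protocol text, one extra table and one listing. The 151 and 190 are unchanged, as are visits and data collection. The downside is that a few truly ineligible hips stay in the primary set, so the rate may be slightly less favourable. The change does not reach already-implanted patients who are never offered consent, since they are outside any consented set.
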